## **AIM 2: Develop tools for translating HRCA to equivalent validated measures of swallowing impairment.**

**A2.a. Introduction:** We have successfully demonstrated HRCA's capabilities in grossly identifying pathological airway protection. However, HRCA's predictive capabilities lie in its ability to analyze the summation of all concurrent events occurring during swallowing. The objective of this aim is to equate, or elicit means of translating, HRCA signal analysis results to a validated clinical measure of swallowing impairment, namely, the Modified Barium Swallow Impairment Profile (MBSImP) [117]. To attain the objective of this aim, we will test the working hypothesis that HRCA can noninvasively quantify levels of dysphagia severity and airway protection comparably to accepted clinical OPD severity scales derived from gold standard VF data analysis. We will use an approach that relies on scoring each swallow in our large dataset according to the MBSImP component scales. Next, through advanced data analytics tools, we will establish relationships between HRCA signal features and the MBSImP scores for each swallow. The rationale for this aim is that HRCA signal analysis results must be equated with and translatable to an acceptable gold standard of swallowing impairment to validate its efficacy in identifying clinically significant dysphagia. We expect that achievement of this aim will substantially advance dysphagia screening and diagnostics by producing a readily deployable surrogate determination of swallowing disability in the absence or inaccessibility of gold standard VF testing.

**A2.b. Justification and feasibility – Review of relevant literature:** To accomplish our goal, it is necessary to equate HRCA signals to standardized and validated measures of swallow impairment and airway protection. As discussed in A1.b, the PAS differentiates normal vs. disordered airway protection [81]. More recently, the MBSImP has become widely accepted in both clinical and research domains as the gold standard for interpreting VF data to determine the degree of swallowing impairment in people with OPD [118]. MBSImP measures 17 components of swallowing impairment in oral, pharyngeal, and esophageal regions through analysis of VF data using ordinal severity scales of 17 components: six oral, ten pharyngeal, and one esophageal. Each component is rated based on specific criteria that were established and validated through expert consensus and repeated testing. Establishing HRCA signal features that predict MBSImP ratings can demonstrate the value of HRCA in the screening and diagnostic processes and potentially obviating the need for VF in some cases. Furthermore, combining MBSImP and PAS [81, 109, 119] leads to a complete multidimensional profile of swallow impairment and potential dysphagia-related risk to which HRCA can be equated. MBSImP has been used concurrently in several studies with PAS and both measures have shown their complementary value in the comprehensive quantification of swallow impairment and the airway protection outcomes that these impairments produce [118, 120-124].

**A2.c. Justification and feasibility – Preliminary studies:** Our pilot study has identified strong differences in clusters of HRCA signal features that clearly separated less- and more-severely impaired swallows. We analyzed 100 swallows from our 274-patient data set, to determine if HRCA signal features can detect swallow kinematic events. All 100 swallows were simultaneously observed with VF and HRCA sensors, and 13 swallow

kinematic events (onset of barium entering pharynx, onset, offset and arrival at maximum displacement of the hyoid bone, onset and offset of laryngeal closure, onset of laryngeal reopening, onset and offset of UES opening, onset of UES reclosure, onset and offset of contact of the tongue base to the posterior pharyngeal wall, and first re-opening of tongue base to posterior pharyngeal wall contact) were measured by judges who were trained in VF image processing methods, blinded to patient diagnosis, and whose inter- and intra-rater reliability were acceptable. The results were compared to HRCA signals to determine the frequency of occurrence of 7 separate HRCA signal feature peaks (maxima) with each of the 13 swallow kinematic events, to a tolerance of within 0.1 seconds of the actual swallow kinematic events, the standard tolerance for temporal VF analysis [89], (Table 2). Fifty-two to 88% of the kinematic events were detected within this tolerance by HRCA sensors more than half of the time. Since the probability is <8% that any continuous vibratory or acoustic signal would exhibit a strongly systematic change that co-occurs with specific swallow kinematic events, these findings indicate that HRCA signal features are strongly associated with swallow kinematic events and may show promise in identifying abnormal vs. normal swallow function. We then stratified the data into two PAS score ranges: 1-2 (normal airway protection) and 3-8 (abnormal airway protection). Microphone and accelerometer signal feature peaks co-occurred with normal airway protection 40-49% of the time, but these peaks co-occurred only 11-14% of the time during abnormal airway protection swallows. Moreover, the ranges of these probabilities did not overlap for any of the four data collection channels, and the results were statistically significant as expected at  $p=0.018$ . These results indicate that HRCA can detect co-occurring swallow kinematic events while at the same time differentiating between normal and abnormal airway protection. Though these results indicate HRCA's ability to detect simultaneously occurring swallowing events and airway compromise in the presence of other noise, the necessary next step is to equate this capability to standard measures of overall swallow impairment.

[figure not shown]
**Table 2 –** Frequency of signal maxima co-occurring with swallow kinematic events; separated by PAS ranges PAS 1-2 vs. PAS 3-8. NUME denotes the number of signal maxima co-occurred with swallow kinematic events > 50% of the time. MIC denotes a microphone, while S-I, A-P, and M-L denote vibrations in superior-inferior, anterior-posterior, and medial-lateral directions captured by an accelerometer.

Sensor	NUME	PAS 1-2		PAS 3-8	
		overall %	range	overall %	range
MIC	80/91	49	37-65	13.6	10-18
S-I	64/91	45	29-62	11	7-16
A-P	55/91	43	26-62	11	6-17
M-L	48/91	40	25-61	10	3-16

**A2.d. Experimental approach:** STEP 1: All swallows from patients and healthy participants (Aim 1) will be rated using the MBSImP. Judges will undergo standardized training in visual inspection and MBSimP ratings of swallow kinematic functions and impairments, and establishment of inter- and intra-rater reliability before beginning scoring. STEP 2: In addition to MBSimP component 16 (pharyngeal residue), pharyngeal residue (valleculae, pyriform sinuses) will be measured using the Normalized Residue Rating Scale which standardizes areas of barium residue retained in pharyngeal recesses (valleculae, pyriform sinuses) using conversion factors based on individual patient height [112]. STEP 3: We will measure airway compromise using the PAS [109]. STEP 4: Pre-process HRCA recordings per steps taken in previous publications [29, 30, 71] to remove any disturbances and diminish noise in these recordings.

STEP 5: We will develop an algorithm based on the state-of-the-art machine learning concepts whose output will be the differentiation between healthy controls and people with suspected dysphagia whose swallows did not exhibit dysphagia, healthy dysphagic (see Figure 11). Specifically, we will utilize a random 70% training subsample for the deep belief machine learning approach as in our preliminary works [70], and once modeling is complete, use the remaining 30% validation subsample to obtain accuracy estimates devoid of model overfitting.

**A2.e. Data interpretation:** We will employ the same deep learning methods as in Aim 1 for our primary analysis, but instead will employ techniques suitable for categorical, ordinal dependent variables such as MBSimP and PAS. In addition, we will employ regression tree and linear mixed model methods in an effort to obtain simpler

**Figure 11 –** Our proposed experimental and data analysis approach for Aim 2.

means of converting HRCA signals. We will examine performance metrics such as root mean square error and multiple coefficient of determination ( $R^2$ ) to evaluate our score equating models.

**A2.f. Expected outcomes:** The benchmark for success of Aim 2 will be creation of a set of HRCA signal signatures that can be translated to MBSImP, PAS, and pharyngeal retention measures. We anticipate a model can be built with sufficiently high predictive ability so that  $R^2$  and/or root mean square error of score translation is no greater than 5% of the range of the swallowing impairment measure. The major outcome of this aim is that HRCA signal signatures will reflect swallow kinematic and airway protection function and equate to standard measures of swallow impairment which will help us develop the HRCA based Aspirometer as a tool that characterizes and predicts risk of adverse outcomes associated with dysphagia, without imaging.

**A2.g. Challenges and contingency plans:** As in Aim 1, in the highly unlikely event that our VF judges' ratings drift unacceptably, we will increase surveillance on inter- and intra-rater reliability and pull judges from analysis and retrain them to criterion, retest their reliability before placing them back online.

**A2.h. Sample size justification:** The proposed approach is based on nonlinear modeling for which classical sample size calculation procedures are not suitable [125, 126]. As our augmented dataset is expected to contain more than 4000 (existing recordings)+700 (Aim 1) swallows, we strongly believe that it is a sufficient number of swallows as previous publications using similar nonlinear modeling techniques used data sets with a significantly lower number of samples [127-129]. Nonetheless, accounting for an intra-class correlation of 0.7 and a resulting design effect of 3.8 as in Aim 1, and assuming as many as 20 predictors will be needed in a linear model, we will be able to detect statistical significance of an  $R^2$  as small as 0.03 in the training sample and 0.06 in the validation sample with 80% power at  $\alpha=0.05$ .

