**A1.e. Data interpretation:** In STEP 2, [name] will train doctoral students to evaluate all VF dependent variables and establish their inter- and intra-rater reliability (intraclass correlation coefficient above 0.9 for continuous variables and kappa above 0.75 or percent exact agreement above 80% for categorical variables), in the measurement of kinematic event timing, and assignment of P-A and pharyngeal retention/residue scores. They will use ImageJ image processing software, to measure penetration-aspiration scores, and kinematic and pharyngeal retention/residue measures from all swallow recordings in this new set of healthy swallows, and complete the same measurements from the remaining 3900 swallows in our database that did not undergo the complete kinematic analysis that we performed to produce the preliminary data presented in section A2.c. To ensure their judgments do not drift over time, we will perform ongoing reliability measures using the same criteria, through a rolling re-analysis of a randomly selected 10% of analyzed swallow recordings. Then, to understand the accuracy of the developed HRCA analysis algorithm using only the training subsample in STEP 5, we will begin by calculating a confusion matrix [85]. The confusion matrix will be calculated by comparing the algorithm's output with scores from STEP 2. The confusion matrix will be then used to calculate false positives, false negatives, true positives and true negatives, and lastly sensitivity, specificity, predictive values and likelihood ratios for the algorithm. These values will be initially calculated using the leave-one-out approach, but we will then repeat the analysis with 10-fold cross-validation. Then in STEP 5, we will use the number of correctly and incorrectly HRCA-detected swallows to calculate the sensitivity and specificity values, again using the leave-one-out approach (the most exhaustive and computationally expensive cross-validation approach) and 10-fold cross-validation. We have proposed state-of-the-art machine learning methods based on deep learning as our primary analysis, but we will also consider other techniques such as classification tree methods [113], and generalized linear models due to their ability to produce simpler prediction rules for ease of use, cognizant of the potential loss of some accuracy compared to deep learning. Finally, we will use the validation subsample to obtain authoritative measures of accuracy devoid of risks of model overfitting.

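### Aim 2's only numeric performance target puts an upper limit on R², and no minimum R² is stated

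*Combined protocol and SAP*

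**What the plan says.** A2.f opens with a success statement that carries no number: "The benchmark for success of Aim 2 will be creation of a set of HRCA signal signatures that can be translated to MBSImP, PAS". Residue measures are listed there too. The number comes in the next sentence, which is framed as an expectation and begins "We anticipate a model can be built with sufficiently high predictive ability so that". The subject that follows is R², tied to the second metric by and/or, and a single limit serves both: "root mean square error of score translation is no greater than 5% of the range of the swallowing impairment measure". A2.e names RMSE and R² as the metrics for judging the score-equating models but gives no threshold for either. A2.h mentions R² only as a detectable effect. A2.d assigns a random 70% of the data to training and 30% to validation.

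Rater acceptance is set out under Aim 1, in A1.e: "intraclass correlation coefficient above 0.9 for continuous variables and kappa above 0.75 or percent exact agreement above 80% for categorical variables". The tasks to which that rule is applied, among which MBSImP rating does not appear, are given as "measurement of kinematic event timing, and assignment of P-A and pharyngeal retention/residue scores".

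**The concern.** One upper bound, expressed as a share of the scale's span, governs two metrics that run in opposite directions. For RMSE it is meaningful. For R² both the direction and the unit are wrong, so the limit cannot separate a good model from a poor one. The conjunction adds to the problem, because it does not say whether one metric is enough or both are needed.

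This is the only figure against which the translation model's performance can be judged. As written, a team reporting Aim 2 could point to a very low R² as meeting the target, and a reader would have no prespecified minimum with which to disagree.

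A second question is whether the RMSE part is set sensibly relative to the reference standard. Videofluoroscopy scores carry rater error, and a translation error limit close to that error leaves the model little room.

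**Working it through.** The plan does not derive its 5% figure, so there is nothing to reproduce. The check is what the sentence implies.

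**Inputs.** PAS runs from 1 to 8 (A2.c splits it into 1–2 and 3–8), a range of 7. Rater floor for categorical scores: 80% exact agreement, or kappa 0.75 (A1.e). Preliminary spread: 55 of 154 swallows impaired (Table 4), taken as PAS 3 or more, the cut described in A3.c. Planned data: 4000 patient swallows plus 700 healthy swallows (A2.h).

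**1. The limit on PAS.** 0.05 × 7 = 0.35. Read literally, this is both the RMSE limit in points and the cap on R².

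**2. The *or* reading.** R² = 0 is below 0.35, so a model that explains nothing meets the target. For any measure spanning 20 points or more, the literal cap is at least 0.05 × 20 = 1.0, which every model meets.

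**3. The *and* reading.** The best constant prediction has RMSE equal to the outcome SD. If a share p of swallows scores 3 or more and the rest score 2 or less, the SD is at least √[p(1 − p)].
- With p = 55/154 = 0.357: √(0.357 × 0.643) = 0.479 points, or 0.479/7 = 6.8% of range. This exceeds 0.35, so the constant prediction fails.
- Adding 700 healthy swallows, assumed all at 2 or less: p = 0.357 × 4000/4700 = 0.304, and √(0.304 × 0.696) = 0.460. It still fails.

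The literal *and* reading has its own fault. With R² = 1 − RMSE²/SD², a model with RMSE of 0.35 or less has R² of at least 1 − 0.1225/0.2296 = 0.466, or 1 − 0.1225/0.2116 = 0.421 with the healthy swallows added. Both exceed the cap of 0.35. On these spreads a good model would breach the R² limit because it is good.

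**4. Secondary note: RMSE limit against rater error, PAS only.**
- Between two raters at agreement a, with every disagreement one step, the RMS difference is √(1 − a). At a = 0.80: √0.20 = 0.447, or 6.4% of range. The limit of 0.35 is tighter. The two are equal at a = 1 − 0.35² = 0.8775.
- For one rater with independent, zero-mean errors: √(0.20/2) = 0.316.
- If instead each rater errs by one step in the same direction with probability p, then 2p(1 − p) = 0.20 gives p = 0.113, and the error against the true score is √0.113 = 0.336.
- Single-rater error of about 0.32 to 0.34 is therefore just below the limit. A model predicting the true score would have √(0.1225 − 0.100) = 0.15 points left for its own error in the first case, and √(0.1225 − 0.1127) = 0.10 in the second.

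**The case against.** The strongest reply is that this is a drafting slip. The same sentence speaks of high predictive ability, and a share of the range fits RMSE only, so nobody intended to reward a low R². That is a fair reading of intent. It does not supply the missing number: no R² floor can be recovered from A2.e, A2.f or A2.h.

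It can also be said that the figure is an expectation and not a decision rule. This stands. The success statement contains no number, and although Aim 3 applies an algorithm informed by Aims 1 and 2, nothing makes it conditional on the 5% figure.

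Some stronger readings are tempting, but the documents do not support them:

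- A reader might infer that the plan sets R² at 5% or less. It says 5% of the measure's range, which is 0.35 for PAS.
- A reader might connect this with A2.h, where R² values "as small as 0.03 in the training sample and 0.06 in the validation sample with 80% power" are called detectable, and conclude that the plan treats them as success. They are minimum detectable effects in a supplementary linear-model calculation.
- A reader might infer that the RMSE target cannot be met because raters may differ by more. A between-rater difference contains two raters' errors, whereas the model is compared with one score. Also, 80% is a floor, so accepted raters may agree better.
- A reader might extend the rater comparison to every measure. The documents give no numeric ranges for the MBSImP components, and Aim 2 sets no numeric threshold for MBSImP raters. For continuous residue at an intraclass correlation of 0.9, the between-rater difference exceeds 5% of range only if the SD is above 0.05/√0.20 = 11.2% of range, and no SD is given. For summed MBSImP scores the comparison can go either way.

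**Conclusion.** The R² part of the target is wrong as written, in direction and in unit, and Aim 2 has no minimum R². This follows from the wording alone and needs no assumption. That a model with no predictive value meets the target holds only if *or* is meant. If *and* is meant, a constant prediction fails on PAS, assuming the preliminary 55/154 split is representative.

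The RMSE part has the right form. On PAS it is very demanding: 0.35 against about 0.447 between raters at the agreement floor, but still above single-rater error of 0.32 to 0.34. Those figures assume one-step disagreements and independent rater errors. If raters qualify through the kappa 0.75 route instead, the between-rater figure runs from 0.34 to 0.47 depending on the assumed score distribution.

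This is a correction that should be made. It is inexpensive and does not undermine the Aim 2 design.

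**What to change.** Replace the sentence in A2.f with two separate criteria, both to be met in the 30% validation subsample:

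1. R² no less than a prespecified floor.
2. RMSE no greater than a stated percentage of the range, given for each measure.

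Delete the and/or. The floor is the team's to choose and justify. As a guide, an RMSE of 5% of range corresponds to R² = 1 − (0.05/s)², where s is the SD as a fraction of range: 0.96 if the SD is a quarter of the range, 0.91 if a sixth, 0.75 if a tenth (all SDs assumed). The floor therefore matters most for measures with little spread.

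Report achieved RMSE for PAS beside the inter-rater RMSE observed in the rolling 10% re-analysis (A1.e). Report it as context and not as the limit, since a limit set at observed rater error would become easier to meet as raters agreed less.

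The cost is wording. The downside is that the stated target becomes harder to meet, because a single metric will no longer be enough.

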**AIM 2: Translate and equate HRCA swallow signal signatures to validated measures of swallowing impairment. Hypothesis: HRCA cutoffs will be significantly associated with validated VF-derived OPD impairment cutoffs.** Accomplishment of this aim positions us to establish independent HRCA cutoffs for levels of OPD severity that differentiate clinically significant OPD and aspiration from benign swallowing impairments.

**AIM 3: Prospectively assess the effectiveness of our HRCA system in predicting clinically significant OPD and aspiration in a randomized, controlled trial. Hypothesis: HRCA, will detect significantly more OPD and significantly more non-OPD, compared to SIS alone.** For this major step, we will deploy combinations of HRCA and SIS with consenting patients, and compare all screening predictions (SIS, HRCA, SIS + HRCA) to VF data from all participants.

[figure not shown]
The outcome of this research will be a clinically accurate, inexpensive, and noninvasive HRCA screening tool that will fundamentally advance efforts to reduce morbidity and mortality caused by OPD. The positive translational impact of this work is the melding of engineering (HRCA) with the clinical (SIS) screening processes. This major technological leap will elevate the current standard of patient care by ensuring that patients with OPD are correctly identified before adverse events can occur, patients without OPD are not unnecessarily deprived of food more accurately than current methods, as well as lowering health care expenditures and lengths of stay and improving quality of lives.

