
**A1.f. Expected outcomes:** The benchmark for success of Aim 1 will be creation of a machine learning algorithm that completes the continuum of of HRCA signal characteristics from normal to the most severely impaired swallowing function that will then be available for future research. Specifically, we anticipate these algorithms

will correctly identify normal airway protection (PAS scores of 1-2) in healthy controls and patients with dysphagia with over 90% accuracy compared to the gold standard VF ratings for each swallow [70]. These outcomes will establish the evidence that the HRCA signals and advanced analytics form a robust and reliable swallowing screening system with comparable accuracy to VF, while also demonstrating the system's ability to identify additional swallowing diagnostic features that are currently only possible with VF, potentially advancing HRCA as not a screening tool with diagnostic capabilities far beyond SIS.

**A1.g. Challenges and contingency plans:** The preliminary results (see A1.c.) strongly support our hypothesis (see A1.a.). In the highly unlikely event that our VF judges' ratings drift unacceptably, we will increase surveillance on inter- and intra-rater reliability and pull judges from analysis and retrain them to criterion, retest their reliability before placing them back online.

**A1.h. Sample size justification:** We currently have data on 4000 swallows from 274 dysphagic persons. We plan to add 700 swallows from 70 healthy persons to this data set. Allowing for some refusals, we anticipate obtaining 650 swallows from 65 healthy persons. Assuming the sensitivity and specificity will be approximately 90%, intra-class correlation of 0.7 from our prior data and a resulting design effect of 3.8 [114], and using published methods [115, 116] implemented in commercially available software (PASS 2012, Number Cruncher Statistical Systems, Kaysville, UT), conservatively we will be able to estimate sensitivity with a margin of error as small as  $\pm 2\%$  and specificity with  $\pm 8\%$  in the training sample, and  $\pm 3\%$  and  $\pm 13\%$  in the validation samples, at the 95% confidence level.

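### Aim 2 is meant to grade dysphagia severity, but its R² is powered on patient and volunteer swallows pooled and no within-patient figure is planned, so part of a reported R² may only reflect telling the two groups apart

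*Combined protocol and SAP*

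**What the plan says.** Under Specific Aims, Aim 2 is to lead to HRCA cutoffs for "levels of OPD severity that differentiate clinically significant OPD and aspiration from benign swallowing impairments". A2.a gives the working hypothesis as quantifying levels of severity and airway protection comparably to VF-based scales. Both are statements about grading impairment.

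The data are pooled. A2.d STEP 1 says "All swallows from patients and healthy participants (Aim 1) will be rated using the MBSImP", and STEP 5 says "we will utilize a random 70% training subsample for the deep belief machine learning approach", with the other 30% kept for validation. A2.h justifies the sample size with "As our augmented dataset is expected to contain more than 4000 (existing recordings)+700 (Aim 1) swallows". It then gives a linear-model calculation with ICC 0.7, design effect 3.8 and 20 predictors: detectable R² of 0.03 in training and 0.06 in validation, with 80% power at α = 0.05.

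On evaluation, A2.e says "We will examine performance metrics such as root mean square error and multiple coefficient of determination". A2.f anticipates R² and/or "root mean square error of score translation is no greater than 5% of the range of the swallowing impairment measure". No section asks for these figures in patients, by group, or against a model that knows only group membership. Aim 3 (A3.d) enrols patients eligible for SIS and applies the Aim 1 and 2 findings to them.

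**The concern.** R² depends on the spread of the outcome in the sample. Adding a block of near-normal swallows to a patient sample creates between-group variance, and any model that partly recognises volunteers explains some of it. That would happen even if the model ranked no patient correctly against another.

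Aim 1 already addresses the healthy end of the continuum. What Aim 2 must add is that HRCA tracks MBSImP, PAS and residue scores among people with suspected OPD, because that is where clinically significant impairment has to be told from benign impairment, and where Aim 3 uses the output. A single pooled R² cannot show how much of it bears on that question.

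**Working it through.** **Inputs.** 4000 patient swallows from 274 persons (A1.h: "We currently have data on 4000 swallows from 274 dysphagic persons"); 700 volunteer swallows (A2.h), or 650 after refusals (A1.h: "we anticipate obtaining 650 swallows from 65 healthy persons"); 70/30 split (A2.d); ICC 0.7, design effect 3.8 and 20 predictors (A2.h); best-network sensitivity 85.7% and specificity 96.9% (A1.c, Figure 9). The documents give no MBSImP means or SDs by group, so d is an assumption and a range is shown.

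**1. The plan's own figure.** Overall F test, noncentral F with 20 and N − 21 degrees of freedom, noncentrality N·R²/(1 − R²), N = swallows × split / design effect.

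| Swallows | Design effect | N (training / validation) | Detectable R² |
|---|---|---|---|
| 4700 pooled | 3.8 | 866 / 371 | 0.024 / 0.056 |
| 4000 patients | 3.8 | 737 / 316 | 0.028 / 0.065 |

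Rounded up to two decimals, the pooled set gives the stated 0.03 and 0.06, and the patient set gives 0.03 and 0.07. The stated figures fit the pooled set, as the wording of A2.h implies.

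**2. Ceiling on the group contribution.** Volunteer share p = 700/4700 = 0.149, so p(1 − p) = 0.127. With equal within-group SDs and perfect recognition of volunteers,

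R² = 0.127d² / (1 + 0.127d²).

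**3. Allowing for imperfect recognition.** The ceiling is multiplied by the squared correlation between true and predicted group, p(1 − p)(a − b)² / [q(1 − q)]. Here a and b are the probabilities that a volunteer and a patient are labelled volunteer, and q = pa + (1 − p)b. Errors are taken as unrelated to severity. Figure 9 does not say which group counts as positive, so both readings are used:

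- a = 0.969, b = 0.143: q = 0.266, factor 0.44.
- a = 0.857, b = 0.031: q = 0.154, factor 0.66.

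| d | Ceiling | With A1.c accuracy |
|---|---|---|
| 0.5 | 0.031 | 0.014–0.020 |
| 1.0 | 0.112 | 0.050–0.075 |
| 1.5 | 0.222 | 0.098–0.147 |

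With 650 volunteer swallows the ceilings at d = 0.5 and 1 are 0.029 and 0.107. If the volunteers' SD is half the patients' and d is in patient SDs, they are 0.034 and 0.125.

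**4. Does such a model grade patients?** In a simulation with 274 patients, 70 volunteers, ICC 0.7 and d = 1, a model that output only group means had validation R² of 0.114 in the pooled data and −0.001 among patients.

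**5. Illustration from the documents.** Table 4 has 55/154 = 35.7% of patient swallows impaired (PAS ≥ 3). A1.b reports one of 95 healthy participants scoring 3 and none higher, about 1.1%. Group membership alone then gives a ceiling of R² = 0.072, or 0.03–0.05 with the factors in step 3. The sources differ and the healthy count is per participant, so this shows only the order of size.

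**6. RMSE.** Even with zero error on every volunteer swallow, pooled RMSE = √(4000/4700) = 0.92 of patient RMSE. A pooled 5% of range therefore means at most 5/0.92 = 5.4% in patients. In the illustration of step 5 (PAS dichotomised at 3), a group-only model has RMSE of about 44% of range.

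**7. Power on patients alone.** A design effect of 3.8 at ICC 0.7 implies 1 + 0.7(m − 1) = 3.8, so m = 5 swallows per person. The plan's counts give 4000/274 = 14.6, hence 1 + 0.7 × 13.6 = 10.5. Then N = 266 (training) and 114 (validation), and detectable R² is about 0.08 and 0.18.

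**The case against.** A reader might infer that a model with no information on severity could have Aim 2 declared a success because it reaches 0.03 or 0.06. The documents do not support that. Those values are the smallest R² detectable with 80% power, from a fallback calculation placed after a statement that classical sample-size methods do not suit the planned modelling. The quantified benchmark in A2.f is the 5%-of-range error, which a group-only model would miss by a wide margin. The hypothesis under Specific Aims is an association between HRCA cutoffs and VF cutoffs, not a significant overall R². It would also be wrong to infer that pooling materially flatters RMSE; step 6 limits the effect to about 8%.

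Other points on the plan's side also stand:

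- Pooling is deliberate. The project wants one continuum from unimpaired to severe, and A2.d STEP 5 itself lists separating healthy controls from patients as an output.
- The wording in A2.e is open-ended and does not exclude figures by group.
- Volunteers are age matched. With similar recording conditions, a model that recognises them from how they swallow would tend to carry some severity information among patients too. A2.c already reports a difference between PAS 1–2 and 3–8 in 100 swallows from the patient set (p = 0.018).
- Aim 3 tests the tool against VF in patients only and should expose a model with no within-patient information.

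These points limit the consequence but do not supply the missing figure. The A2.f wording, R² and/or RMSE within 5% of range, sets no usable bar for R². Aim 3 comes after the Aim 2 conclusion, in about 46 patients.

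**Conclusion.** The point holds as a limit on what a pooled R² can show. Part of it can reflect the difference between volunteers and patients, and the plan names no figure that separates this from severity grading in patients. With equal SDs, the group contribution is at most about 0.03 at d = 0.5 and 0.11 at d = 1; with A1.c accuracy it is about 0.01–0.02 and 0.05–0.07. These sizes rest on an assumed d and, for the lower ranges, on recognition errors unrelated to severity. RMSE is little affected. The documents do not show that Aim 2 would be declared supported by a model that cannot grade patients. This is an inexpensive improvement to the evaluation; it does not invalidate pooling for model building.

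**What to change.** In A2.e and A2.f, state that R² and RMSE computed on patient swallows, in both training and validation samples, are the evidence for severity grading. Report the volunteer and pooled figures beside them. A model using only a group indicator is a useful baseline for the pooled figure. Volunteers stay in model building.

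If A2.h is restated for patients, do not carry the 3.8 forward to obtain 0.03 and 0.07. Use a design effect that matches the swallows per person: about 10.5 at ICC 0.7, giving detectable R² of about 0.08 (training) and 0.18 (validation).

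The cost is a sentence or two and, if power is restated, one recalculation. No new data are needed. The reported R² is likely to look less favourable, and the restated detectable values are larger than those now in the plan.
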